### **5.3 Monitoring and Toxicity Management**

Each patient receiving nivolumab will be evaluable for safety. The safety parameters include all laboratory tests and hematological abnormalities, physical findings, and spontaneous reports of adverse events reported to the investigator by patients.

Each patient will be assessed periodically for the development of any toxicity. Toxicity will be assessed according to the NCI CTCAE v5.0. Dose adjustments will be made according to the system showing the greatest degree of toxicity.

Management of any grade 3 or higher toxicity should be discussed with the PI of the study.

### **5.4 Permitted Concomitant Therapy Requiring Caution and/or Action**

All concomitant medications used by the subject (including prescription and over-the-counter medications, transfusions, vitamins, herbal remedies, and nutritional supplements) during the period from 30 days before the first dose of study treatment through 30 days after the date of the last dose of study treatment are to be recorded in the case report forms.

- Antiemetics and antidiarrheal medications are allowed in accordance to standard clinical practice if clinically indicated;
- Granulocyte colony-stimulating factors (G-CSF or GM-CSF) are generally not to be used in this protocol. Note that hematologic growth factors are not allowed during concurrent cisplatin and radiation treatment. If hematologic growth factors must be used outside of the radiation phase of treatment, they should be used per clinical guidelines (eg, American Society of Clinical Oncology [ASCO] or [European Society for Medical Oncology] ESMO guidelines);
- Transfusions, hormone replacement, and short term higher doses of corticosteroids should be utilized as indicated by standard clinical practice

### **5.5 Prohibited Concomitant Therapy**

The following medications are prohibited during the treatment and follow-up phases (before recurrence) of the study (unless utilized to treat a drug-related adverse event):

- Immunosuppressive agents
- Immunosuppressive doses of systemic corticosteroids (except as stated in Section 5.4)
- Any concurrent anti-neoplastic therapy (including, but not limited to chemotherapy, hormonal therapy, immunotherapy, or radiation therapy), other than those allowed in the protocol.

### 5.5.1 Other Anticancer or Investigational Therapies

No other anti-cancer therapies (including non-platinum chemotherapy, radiation, hormonal treatment [except Corticosteroids, bisphosphonates, or denosumab], antibody or other immunotherapy or other experimental drugs) of any kind will be permitted while the patient is participating in the study.

Patients experiencing unacceptable toxicity due to cisplatin may be switched to carboplatin by the treating physician after consulting with the Study Chair. Carboplatin should be administered weekly at AUC 2, further modifications to the regimen should be discussed with the study chair.

### 5.5.2 Hormonal Contraception Allowed/Excluded

The use of oral contraceptives is allowed during the study.

## 6 Study Procedures and Observations

### 6.1 Schedule of Procedures and Observations

The study-specific assessments are detailed in this section and outlined in [Section 6 Schedule of Study Procedures and Assessments](#). Screening assessments must be performed within 30 days prior to the first dose of investigational product. Any results falling outside of the reference ranges may be repeated at the discretion of the investigator. All on-study visit procedures are allowed **a window of  $\pm$  3 days** unless otherwise noted. Treatment or visit delays for public holidays or weather conditions do not constitute a protocol violation.

A written, signed, informed consent form (ICF) and a Health Insurance Portability and Accountability Act (HIPAA) authorization must be obtained before any study-specific assessments are initiated. A copy of the signed ICF will be given to the subject and a copy will be filed in the medical record. The original will be kept on file with the study records.

All patients who are consented will be registered in OnCore®, the UCSF Helen Diller Family Comprehensive Cancer Center Clinical Trial Management System (CTMS). The system is password protected and meets HIPAA requirements.

#### 6.1.1 Pretreatment Period

During the Pre-Treatment Period, subjects are consented and qualified (screened) for the study. Informed consent must be obtained before initiation of any clinical screening procedure that is performed solely for the purpose of determining eligibility for this study. Evaluations performed as part of routine care before informed consent can be considered as screening evaluations if done within the defined screening period, and if permitted by the site's institutional review board (IRB)/ethics committee (EC) policies.

Study eligibility is based on meeting all of the study inclusion criteria and none of the exclusion criteria at screening and on Study Day 1 before study treatment administration. The following assessments will be conducted before subjects receiving their first dose of nivolumab on this protocol:

##### 6.1.1.1 Screening Assessments

Patients will undergo screening assessments within 30 days before receiving the first dose of nivolumab, unless otherwise noted. Study procedure-related AEs that occur after signing of the

Informed Consent Form (ICF) and before administration of nivolumab will also be collected.

The Screening procedures and assessments must be completed within 30 days prior to the Cycle 1 Day 1 Visit, unless otherwise noted.

- Physical examination
- Weight
- Vital signs
- Complete medical history
- Baseline conditions assessment
- Disease Assessment
- ECOG Performance status
- History of prior treatments and any residual toxicity relating to prior treatment
- Concomitant medications and procedures
- Biopsy or archived tissue procurement
  - Archived tissue: If no intervening treatment received, adequate tissue available, and performed within 90 days of day 1 (cycle 1 day 1) of study treatment; otherwise, fresh biopsy required. See Appendix 4.
- Complete blood count (CBC) with differential and platelet count (within 14 days of Cycle 1 Day 1)
- Serum chemistry assessment (within 14 days of Cycle 1 Day 1), including:
  - Alkaline phosphatase, aspartate aminotransferase/alanine aminotransferase (ALT/AST), total bilirubin, total protein, albumin, calcium, phosphorus, magnesium, blood urea nitrogen (BUN), creatinine, glucose (fasting), potassium, sodium, chloride, bicarbonate, uric acid, LDH, fasting lipid panel (LDL, total cholesterol, triglycerides).
- Serum or urine pregnancy test within 7 days prior to the start of study drug in pre-menopausal females.
- TSH evaluation (within 14 days of Cycle 1 Day 1)
- Urinalysis (within 14 days of Cycle 1 Day 1)
- MRI of nasopharynx, face, and neck within 60 days prior to start of study drug.
- Whole body PET-CT of top of head to mid-thigh (preferred) or CT of chest, abdomen, and pelvis within 60 days prior to the start of study drug.
- Research blood draw: collection of peripheral blood for EBV DNA and correlative biomarker studies.
- All blood draws may be done within 7 days prior to start of therapy unless otherwise specified.
- Contraceptive counseling
- Serum pregnancy test (by local laboratory) ≤ 1 days prior to the first day of dosing for women of childbearing potential. If the serum pregnancy test results are not available on C1D1, a urine pregnancy test can be performed on C1D1 to confirm that the patient is not pregnant prior to dosing.
- Baseline quality of life assessments

For each subject, the Pre-Treatment Period ends upon receipt of the first dose of study treatment or final determination that the subject is ineligible for the study.

The following assessments are not required but highly recommended:

- Audiogram;
- Speech and swallowing consultation with formal assessment by modified barium swallow;
- Dental evaluation and counseling in preparation for radiation therapy;
- Nutritional evaluation

### **6.1.2 Treatment Period**

During the Treatment Period subjects will receive nivolumab until the period of adjuvant therapy is complete, disease progression, the occurrence of unacceptable drug-related toxicity or for other reason(s) such as subject withdrawal. Subjects should be instructed to immediately inform the principal investigator (PI) of any AEs. Patients will be monitored for AEs from the time the first dose of nivolumab is administered through 30 days after the last dose.

Nivolumab will be administered to patients every 2 weeks through the intravenous route. Each 14-day period of treatment represents 1 cycle, with dosing initiated on C1D1. No dose escalation beyond the starting dose is allowed.

Patients will undergo serial assessments for anti-tumor efficacy and drug safety. Tumor samples will be collected at baseline and after the first cycle of nivolumab at the investigator's discretion. Serial blood sampling will be conducted for longitudinal immunologic assessment (see Appendix 4). Radiologic scans will be acquired by the investigative site and evaluated locally for patient treatment decisions. Patients will be followed with monthly clinical and laboratory assessments while on protocol-mandated treatment, as well as routine physical examinations every 3 months and scans at the end of treatment and 12 months to assess for disease status for a 1 year period following completion of all treatment.

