Duration of Therapy	Patients will receive 23 weeks of an anticipated total therapy course, although the duration for an individual patient may be extended to as long as 33 weeks to allow for resolution of toxicities.
Duration of Follow-up	Follow-up visits will occur at 1, 3, 6, 9, and 12 months for up to 12 months after end of treatment. Survival follow-up information may be collected via telephone calls or medical records review for an additional 4 years . Survival and disease status will be collected during this 5-year period until participant death, withdrawal, or if the participant is lost to follow-up.
Duration of study	The study will reach completion in 6 years from the time the study opens to accrual.
Study Drugs	Nivolumab will be administered intravenously, at a dose of 240 mg every 14 days. Nivolumab may be held for toxicity but there are no dose reductions.
Safety Assessments	Analyses will be performed for all patients having received at least one dose of study drug. The study will use the CTCAE v5.0 for reporting of non-hematologic adverse events and modified criteria for immune related adverse events. Safety assessments will consist of monitoring and reporting adverse events (AEs) and serious adverse events (SAEs) that are considered related to nivolumab, all events of death, and any study specific issue of concern. The study period during which all AEs and SAEs must be reported begins after informed consent is obtained and study treatment is initiated and ends 12 months following the last administration of study treatment or study discontinuation/termination, whichever is earlier.
Efficacy Assessments	The primary measure of feasibility will be the rate of completion of all adjuvant therapy. This will be determined based on ability to complete all 6 cycles of adjuvant nivolumab without discontinuation for disease progression or toxicity. Secondary measures of efficacy will be clinical response as judged by the investigator; ORR by RECIST 1.1; locoregional control rate, distant metastasis rate, overall survival rate determined by standard physical examination and radiologic imaging; the rate of EBV DNA clearance at end-chemoradiation and at 1 year post-treatment as determined by PCR assay; toxicity assessments graded by CTCAE v5.0 and modified immune related criteria; and quality of life by FACT-NP, FACT-Taxane, HHIE-S, and EuroQOL EQ-5D-3L. Exploratory assessments are self-explanatory.

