### 3.7 Duration of Follow Up

Patients will be followed for safety assessments for 100 days after completion of treatment or removal from study, or until death, whichever occurs first. All SAEs must be collected that occur within 100 days of discontinuation of dosing. Patients removed from study for unacceptable treatment related adverse event(s) will be followed until resolution or stabilization of all treatment related adverse events to Grade 2 or lower. Patients will be followed for adverse events for up to 1 year. Survival and disease status information may also be collected from review of the electronic medical records, patient visits, or telephone calls. Survival and disease status will be collected until participant death, withdrawal, or if the participant is lost to follow-up.

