#### 7.4 Recording of an Adverse Event

Grade 1-5 adverse events will be entered into OnCore®, whether or not the event is believed to be associated with use of the study drug. Data about these events and their severity will be recorded using the NCI CTCAE v5.0.

The Investigator will assign attribution of the possible association of the event with use of the investigational drug, and this information will be entered into OnCore® using the classification system listed below:

Relationship	Attribution	Description
Unrelated to investigational drug/intervention	Unrelated	The AE is clearly NOT related to the intervention
	Unlikely	The AE is doubtfully related to the intervention
Related to investigational drug/intervention	Possible	The AE may be related to the intervention
	Probable	The AE is likely related to the intervention
	Definite	The AE is clearly related to the intervention

Signs or symptoms reported as adverse events will be graded and recorded by the Investigator according to the CTCAE. When specific adverse events are not listed in the CTCAE they will be graded by the Investigator as *none*, *mild*, *moderate* or *severe* according to the following grades and definitions:

- Grade 0 No AE (or within normal limits)
- Grade 1 Mild; asymptomatic or mild symptoms; clinical or diagnostic observations only; intervention not indicated
- Grade 2 Moderate; minimal, local, or noninvasive intervention (e.g., packing, cautery) indicated; limiting age-appropriate instrumental activities of daily living (ADL)
- Grade 3: Severe or medically significant but not immediately life-threatening; hospitalization or prolongation of hospitalization indicated; disabling; limiting self-care ADL
- Grade 4: Life-threatening consequences; urgent intervention indicated
- Grade 5: Death related to AE

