### **Nonserious Adverse Event Collection and Reporting**

The collection of nonserious AE information should begin at initiation of study drug. All nonserious adverse events (not only those deemed to be treatment-related) should be collected continuously during the treatment period and for a minimum of 100 days following the last dose of study treatment.

Nonserious AEs should be followed to resolution or stabilization, or reported as SAEs if they become serious. Follow-up is also required for nonserious AEs that cause interruption or discontinuation of study drug and for those present at the end of study treatment as appropriate.

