#### 8.1.2 Secondary Endpoints

**Efficacy:** ORR as assessed by the study investigator by RECIST 1.1 criteria. The ORR is defined as the best overall response (BOR) recorded from the first day of treatment until time of assessment.

**Safety and tolerability:** Evaluate the number and frequency of Adverse Events (AEs) as determined by National Cancer Institute Common Toxicity Criteria (NCI-CTC) version 4.0 by investigator assessment.

- To determine the clinical response as judged by the investigator;
- To determine the overall response rate from the first day of treatment to 1 year post-treatment, as determined by RECIST 1.1 criteria;
- To determine the locoregional control rate at 1 year post-treatment;
- To determine the distant metastasis rate at 1 year post-treatment;
- ;
- To determine the rate of EBV DNA clearance at end of chemoradiation and at 1 year post-treatment;  
To determine the acute and late toxicity rates according to CTCAE v5.0, including immune-related adverse events (AEs);
- To assess patients' quality of life from baseline through 1 year post-treatment;

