### 8.5 Evaluation of Safety

Safety analyses will be performed for all patients having received at least one dose of study drug. The study will use the NCI CTCAE v5.0.

The safety population will consist of all subjects who receive any amount of study treatment. Safety will be assessed by evaluation of AEs. All safety analyses will be performed using the safety population. Adverse event terms recorded on the CRFs will be mapped to preferred terms using the Medical Dictionary for Regulatory Activities (MedDRA). Seriousness, severity grade and relationship to study treatment will be assessed by the investigator. Severity grade will be defined by the National Cancer Institute (NCI) CTCAE v5.0. Listings of AEs will be provided.

Separate tables will present the following by dose group and study phase:

- All treatment-emergent AEs
- Treatment-emergent AEs by CTCAE grade
- Grade 3 or greater treatment-emergent AEs
- Treatment-related, treatment-emergent AEs
- Dose-limiting toxicity AEs
- Serious treatment-emergent AEs
- Treatment-emergent AEs with an outcome of death
- Treatment-emergent AEs leading to discontinuation of nivolumab.
- Treatment-emergent AEs resulting in interruption or reduction or delay of nivolumab.

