### **Adverse Event Review and Monitoring**

### Adverse Event Monitoring

All Grade 3-5 Adverse Events, whether or not unexpected, and whether or not considered to be associated with the use of study drug, will be entered into OnCore®, UCSF's Clinical Trial Management System.

All Grade 3-5 adverse events entered into OnCore® will be reviewed on a monthly basis at the UCSF Site Committee meetings. All clinically significant adverse events must be reported to the UCSF Coordinating Center by the participating sites within 10 business days of becoming aware of the event or during the next scheduled quarterly conference call, whichever is sooner. The UCSF Site Committee will review and discuss the selected toxicity, the toxicity grade, and the attribution of relationship of the adverse event to the administration of the study drug(s) from the UCSF Coordinating Center and the participating sites.

In addition, all suspected adverse reactions considered "serious" must be entered in OnCore® and reported to the UCSF Coordinating Center within 1 business day. The suspected adverse reactions considered "serious" will be reviewed and monitored by the Data and Safety Monitoring Committee on an ongoing basis and discussed at the DSMC meeting, which take place every six (6) weeks.

If a death occurs during the treatment phase of the study or within 30 days after the last administration of the study drug(s) and is determined to be related either to the investigational drug or any research related procedure, the Study Chair at the UCSF Coordinating Center or the assigned designee must be notified within 1 business day from the participating site(s) and the Study Chair must then notify the DSMC Chair or qualified alternate within 1 business day of this notification. The contact may be by phone or e-mail.

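### The rules for collecting the secondary toxicity endpoint contradict each other on follow-up window, grades entered and CTCAE version, and should be reconciled

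*Combined protocol and SAP*

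**What the plan says.** **Window.** Section 6.1.2 states: "Patients will be monitored for AEs from the time the first dose of nivolumab is administered through 30 days after the last dose". Section 6.1.3 and the end-of-treatment footnote to Table 6.1 keep patients under safety follow-up until a visit 28 (± 7) days after the last dose. Section 3.7 sets safety assessments at 100 days and then adds, in the same paragraph, "Patients will be followed for adverse events for up to 1 year". The nonserious-event text under section 7.4 requires collection "for a minimum of 100 days following the last dose of study treatment". The abstract says that the reporting period for all AEs and SAEs "ends 12 months following the last administration of study treatment or study discontinuation/termination, whichever is earlier". Section 6.1.4 lists AE monitoring at follow-up visits to 12 months, though only until progression if that comes sooner. Table 6.1 marks AE assessment in the follow-up column and again in the survival follow-up column.

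**Events entered.** Section 7.4: "Grade 1-5 adverse events will be entered into OnCore". Section 7.6 also enters all AEs and separately has grades 3 to 5 reviewed monthly. In Appendix 2, the run-in plan (item 3.1) calls for entry of clinically significant events. The expansion plan gives the events to be entered as "All Grade 3-5 Adverse Events, whether or not unexpected".

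**Scale.** Section 2.4.2 uses NCI-CTC version 4.0. The safety paragraph of section 8.1.2 counts AEs "as determined by National Cancer Institute Common Toxicity Criteria (NCI-CTC) version 4.0 by investigator assessment", yet a later bullet in 8.1.2 uses v5.0, as does the objective in section 2.2. Section 8.5: "Severity grade will be defined by the National Cancer Institute (NCI) CTCAE v5.0". The dose-delay text in section 5.2.1 spells out version 4.0 and abbreviates it as v5.0 in the same phrase.

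**The concern.** The toxicity endpoint is a set of rates. A rate needs one period at risk, one rule for which events are recorded and one grading scale, and the current text leaves all three open.

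The analysis section does not settle the matter. Section 8.5 tabulates treatment-emergent events, but the documents neither define that term nor give it an end date, so whatever sites collect becomes the endpoint. The trial has several institutions. Sites could apply different windows in good faith, and the pooled late-toxicity rate would then have no common time base.

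Section 8.5 also asks for tables by study phase, including all treatment-emergent events and events by CTCAE grade. The entry rules in Appendix 2 change at that same boundary between run-in and expansion. A difference in low-grade events between the phases could therefore come from recording practice and not from treatment.

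**Working it through.** The documents give no sample size, power or expected rate for toxicity, so there is no stated figure to reproduce. The check sets the rules side by side.

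**1. Which windows truly conflict?** Time after the last nivolumab dose (section 3.7 counts from completion of treatment or removal from study):

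- Section 6.1.3 and Table 6.1 footnote: end-of-treatment visit, 28 − 7 = 21 to 28 + 7 = 35 days.
- Section 6.1.2: 30 days.
- Section 3.7, safety assessments and SAEs: 100 days.
- Section 7.4, nonserious events: at least 100 days.
- Section 3.7, AEs: up to 1 year.
- Abstract, all AEs and SAEs: 12 months, or study discontinuation or termination if earlier.
- Section 6.1.4: visits to 12 months, or to progression.
- Table 6.1: AE assessment marked at follow-up.

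A minimum of 100 days fits inside 12 months, so section 7.4 does not contradict the abstract. The hard conflict is between the stop at about one month (6.1.2, 6.1.3 and the footnote) and the 12-month rules. The 100-day safety sentence in 3.7 can be read as a lower tier, but it does not say so. Section 6.1.4 adds a further open question: whether AE collection ends at progression. Neither the abstract's reporting rule nor the Table 6.1 follow-up footnote contains that limit.

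**2. Where the cut-offs fall.** Take dose schedule 1, with no delays and radiation five days a week from day 15:

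- Last nivolumab, cycle 12 day 1: 1 + 11 × 14 = day 155.
- End of 33 fractions: 15 + 42 + 2 = day 59.
- 30-day cut-off: 155 + 30 = day 185, which is 185 − 59 = 126 days after radiation ends.
- 12-month cut-off: 155 + 365 = day 520, which is 520 − 59 = 461 days after radiation ends.

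A site stopping at day 185 would record nothing from day 186 to day 520, a period of 335 days. That counts days, not events.

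**3. Which entry rule applies?** The main text has one rule for both phases (all grades). Appendix 2 has two others, one per phase, and they differ from each other as well as from the main text. If sites follow Appendix 2, neither phase is assured of complete low-grade data, and the two phases are incomplete in different ways.

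**4. Which version applies?** Version 4.0 appears in 2.4.2 and in the safety paragraph of 8.1.2. Version 5.0 appears in 2.2, in a bullet of 8.1.2, in 5.3, in 7.4, in the Table 6.1 footnotes and in 8.5. Two versions may assign different grades to the same event. The documents give no basis for saying that one yields more events than the other.

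**The case against.** The best reply is that a site reading all of section 6 would not stop at 30 days. The sentence in 6.1.2 concerns the treatment period, 6.1.4 lists AE monitoring at later visits, and Table 6.1 schedules it. That stands, and it is why loss of late events is only a risk. It does not remove the conflict, because 6.1.2 and 6.1.3 state their own end points and do not defer to the table.

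On entry, the expansion plan does not say that only grades 3 to 5 are entered, and it sits in a monitoring appendix. It could be a minimum. That also stands, but sites still have three different instructions. On scale, version 5.0 is used so widely that 4.0 looks like leftover wording, which is likely but leaves the endpoint definition wrong as written.

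Three stronger readings are tempting, and the documents support none of them:

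- A reader might infer that a 30-day window captures only 30/365 = 8% of late toxicity, and 100 days 100/365 = 27%. These are shares of calendar days. The documents give no onset distribution and no boundary between acute and late. The share also depends on the starting point: counted from the end of radiation, the 30-day rule covers 126/461 = 27% of the period.
- A reader might infer that 34 of 40 patients would contribute no low-grade events. That is an upper bound. It assumes the 40-patient design, six run-in patients at the selected schedule and a strict reading of the expansion plan. Sections 8.2.3 and 8.2.4 describe 28 patients instead, of whom at most 22 are in expansion.
- A reader might infer that the version conflict leads to under-counting. It has no established direction.

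**Conclusion.** The contradictions are real and in current text, and no rule of precedence resolves them. If a site follows the 30-day or end-of-treatment rule, late events are missed. If sites follow the Appendix 2 entry rules, low-grade rates may not be comparable between run-in and expansion in the section 8.5 tables. The version conflict makes grading inconsistent but does not bias the count in a known direction.

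No numerical size can be attached, because the effect depends on how sites read the text and on when events occur, and the documents give neither. The affected endpoint is secondary and has no stated test. The rate of completing adjuvant nivolumab, which is the primary endpoint, is not directly affected. The point merits correction because a stated endpoint is exposed and the remedy is cheap.

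**What to change.** - **Window.** Align section 6.1.2, section 6.1.3, the end-of-treatment footnote to Table 6.1 and the 100-day safety sentence in section 3.7 with the 12-month AE window already scheduled. State whether AE collection continues after progression, which section 6.1.4 leaves unclear.
- **Entry.** In both Appendix 2 plans, say that events of all grades are entered and that grades 3 to 5 are reviewed monthly. This matches sections 7.4 and 7.6.
- **Scale.** In sections 2.4.2 and 8.1.2, use the version named in the safety analysis (v5.0).
- **Dose-delay text.** Section 5.2.1 names both versions in one phrase, and grade there governs treatment. The sponsor should reconcile it; this review does not propose which version should apply.

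The changes are wording. The follow-up visits are already scheduled, so the cost is more AE data entry at sites that would otherwise have stopped early or entered only higher grades.
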